SM	Study Medication

SOC	System Organ Class in MedDRA
TEAE	Treatment-emergent adverse event
TLF	Tables, Listings and Figures
WFIRS-P	Weiss Functional Impairment Rating Scale – Parent Version
WHODD	WHO Drug Dictionary

1 Introduction

This document describes the statistical analyses and data presentations to be performed on Study [812P303](#). This Phase III, randomized, multicenter, double-blind, 3-arm, parallel-group, and placebo controlled pivotal study of SPN-812 ER is titled “*Evaluation of SPN-812 ER 200 and 400 mg Efficacy and Safety in Children with ADHD - A Double-Blind, Placebo-Controlled, and Pivotal Trial.*”

The purpose of this statistical analysis plan (SAP) is to ensure the credibility of the study findings by specifying the statistical approaches to the analysis of the data prior to database lock. This SAP covers the planned analyses of all data collected on the eCRFs and diary pages, and will identify handling of data issues. It describes the efficacy and safety variables, anticipated data manipulations, and other details of the analyses not provided in the study protocol. The statistical analysis plan presented in this document will supersede the statistical analysis methods described in the clinical protocol. Any deviations/changes from the planned analyses described in this SAP will be identified, with justification, in the appropriate section of the clinical study report. This SAP is based on the protocol 812P303, Version 4.0, dated 17Sept2018.

2 Study Objectives

2.1 Primary Objective

- To evaluate the efficacy of SPN-812 extended release (ER) compared to placebo as monotherapy for the treatment of ADHD in children (6 -11 years).

2.2 Secondary Objectives

2.2.1 Key Secondary Objectives:

To assess the effect of SPN-812 ER as assessed by:

1. Clinical Global Impression-Improvement (CGI-I)
2. Conners 3rd edition (Conners 3) – parent
3. Weiss Functional Impairment Rating Scale – Parent report (WFIRS-P)

2.2.2 Additional Secondary Objectives:

1. 50% Responder rate in ADHD-RS-5 Total score
2. Parenting Stress Index, Fourth Edition, Short Form (PSI-4-SF)
3. ADHD-RS-5 Inattention/Hyperactivity/Impulsivity subscale scores

4. Conners 3rd edition (Conners 3) – self, composite T-score (ages 8-11)

2.2.3 Exploratory Objectives

- [REDACTED]
- [REDACTED]
- [REDACTED]
- [REDACTED]

2.2.4 Safety Evaluation

- To evaluate the safety and tolerability of SPN-812 ER in children with ADHD

2.2.5 Additional Exploratory Objective

[figure not shown]
- a Redacted
- [REDACTED]
- [REDACTED]
- [REDACTED]

3 Study Description

3.1 Study Design

This is a multicenter, randomized, double-blind, placebo-controlled, 3-arm, parallel-group study, to assess the efficacy and safety of SPN-812 ER as monotherapy for the treatment of children 6-11 years old with ADHD. Approximately 300 subjects will be randomized in a 1:1:1 ratio of placebo or one of the two active treatment arms (SPN-812 ER 200 or 400 mg). Following up to four weeks of screening, subjects will be randomized and undergo three weeks of titration followed by five weeks of maintenance for a total of eight weeks of treatment and total study duration of up to 12 weeks. The study schematic appears in [Figure 1](#).

Figure 1: Design Schematic

Titration to SPN-812 ER 200 mg dose from baseline (Day 1) in the week 1 visit for subjects randomized to SPN-812 ER 200 mg dose by 100 mg. Titration to SPN-812 ER 200 mg, 300 mg, and 400 mg dose from baseline (Day 1) in the week 1, week 2, and week 3 visits, respectively, for subjects randomized to SPN-812 ER 400 mg dose by 100 mg each week.

3.2 Schedule of Visits and Procedures Study

All subjects who are randomized and take any SM will be followed according to the protocol regardless of the number of doses of SM taken, unless consent for follow-up is withdrawn. [Table 1](#) below presents the Schedule of Visits and Procedures for the study.

Table 1: Schedule of Visits and Procedure

Period	Screening	Treatment Phase			
		Titration		Maintenance	
		Baseline, Randomization			End of Study ⁱ
Visit Number	1	2	3, 4	5-9	10
Visit Day		1	7, 14	21, 28, 35, 42, 49	56
Visit Window (days)	≤28d before V2		±2	±2	±2
Informed Consent/Accent (if applicable) ^a	X				
Medical and Psychiatric History	X				
Mini-KID	X				
Demographics	X				
Urine Drug Screen	X				
Randomization		X			
Physical Exam ^b	X				X ^c
Inclusion/Exclusion Criteria	X	X			
ECG (12-lead)	X				X
Vital Signs ^d	X	X	X	X	X
Hematology	X				X
Serum Chemistry	X				X

Pharmacogenomic sample	X				
Urine Pregnancy test, FOCP only		X			X
CGI-S	X	X			
CGI-I			X	X	X
C-SSRS	X	X	X	X	X
ADHD-RS-5	X	X	X	X	X
WFIRS-P, PSI-4-SF		X			X
Conners 3 ^e – parent, self		X			X
Concomitant Medication	X	X	X	X	X
Adverse Events		X ^f	X	X	X ^f
Drug Dispensed		X ^g	X	X	
Drug Return, Compliance			X	X	X
Optional PK Blood Sampling ^h			X	X	X

a To be obtained prior to performing any study procedures.

b Includes height and weight, excludes genitourinary system

c Changes from Screening only

d Seated (5 min) heart rate and blood pressure, temperature, respiratory rate

e Self report = 8-11 year olds only

f At Baseline, AEs are recorded only after SM is administered. Subjects with serious adverse events at EOS will be followed until the event has resolved or considered stable.

g Titration will begin after first dose of SM is administered

- ^h An optional PK substudy will take place between Visits 3 and 10, inclusive. Samples will be taken pre-dose and post-dose at Hours 1, 2, 4, and 6.
- ⁱ EOS or last visit in the case of early discontinuation.

3.3 Procedures for Discontinuing Treatment and Removal of Subjects from Study

Subjects will be considered to have completed the study if they complete all visits up to and including Week 8 (EOS).

All subjects who discontinue early will complete the procedures listed for Week 8 (EOS).

All reasons for screening failure will be recorded. If the subject passes screening but fails eligibility at Baseline, the reason(s) will also be recorded.

The Investigator(s) or subjects themselves may stop SM treatment at any time for safety or personal reasons. A subject is free to withdraw from the study at any time for any reason without prejudice to their future medical care by the physician or at the institution. The Sponsor may also withdraw the subject at any time in the interest of subject safety. The withdrawal of a subject from the study should be discussed where possible with the Medical Monitor and/or Clinical Research Associate (CRA) before the subject stops SM. Subjects removed from the study for any reason will not be replaced.

Reasons for subject discontinuation may include:

- Withdrawal of consent
- Noncompliance
- Occurrence of unmanageable AEs
- Lost to follow-up
- Other

The primary reason for subject discontinuation must be recorded in the subject's medical record and on the eCRF. If a subject is withdrawn for more than one reason, each reason should be documented in the source document and the most medically significant reason should be entered on the eCRF.

If a subject misses doses of SM during this study, the Investigator shall counsel the subject/caregiver on the importance of compliance. If the subject has consistently missed doses, he or she may be discontinued from the study at the discretion of the Investigator and in consultation with the Medical Monitor; all procedures for discontinuation will be followed.

3.4 Study Treatments

3.4.1 Methods of Assigning Subjects to Treatment Group

Eligible subjects will be randomized in a 1:1:1 ratio at Visit 2 (Baseline) and will receive either placebo, SPN-812 ER 200 mg/day, or SPN-812 ER 400 mg/day.

Allocation of study treatment will occur centrally via an interactive web response system (IWRS) using a randomization schedule to determine the kit assignment for each subject being randomized

3.4.2 Treatment, Dose, and Mode of Administration

SPN-812 (Viloxazine hydrochloride extended-release tablet) or matching placebo tablets will be administered orally (PO) once daily (QD). The initial dose may be taken at the clinic during the Baseline Visit, with the next dose taken the next morning. Subjects will be titrated up at 100 mg/week to the final dose (1:1:1) as follows:

Treatment A: Placebo

Treatment B: SPN-812 ER 200 mg/day (2 \times 100 mg SPN-812 ER)

Treatment C: SPN-812 ER 400 mg/day (4 \times 100 mg SPN-812 ER)

3.4.3 Duration of Treatment and Study Duration

Total subject duration on study is approximately 12 weeks.

- Pre-treatment phase: 4 weeks
- Treatment phase: 8 weeks
 - Titration period: 3 weeks
 - Maintenance period: 5 weeks

3.4.4 Blinding

The subject and all personnel involved with the conduct and the interpretation of the study, including the Investigators, study site personnel, the Sponsor and Contract Research Organization (CRO) clinical staff, including the Medical Monitor, will be blinded to the medication codes. A limited number of Supernus personnel will perform and interpret the plasma assays for the population PK analysis and will be aware of these plasma data during the study. These personnel will not have access to the randomization schedule, are not associated with the clinical conduct of the study, and will not reveal to any clinical personnel involved in the study the treatment to which a subject will be assigned. Randomization schedule data will be kept strictly confidential, filed securely by the IWRS vendor, and accessible only to authorized persons until the time of unblinding.

3.5 Sample Size and Power Considerations

Seventy-two subjects per treatment group in the ITT population will yield 90% power at a significance level of 0.05 (two-sided) using a two-sample t-test with equal allocation to the treatment

groups. This assumes an effect size of 0.547, observed in the comparison of SPN-812 200 mg and placebo in the SPN-812 Phase IIb study (based on the CFB to endpoint in the ADHD-RS-IV total score). A total of 300 subjects (100 subjects in each of the three treatment groups) will be randomized to account for an anticipated 27.9% of randomized subjects not completing the study.

4 Definitions and Derivations

1. Baseline: Unless specified otherwise, baseline is defined as the non-missing value collected most recent to and before the time of the very first dose of the SM.
2. The study day (DY) is calculated as Visit date minus Reference date + 1 day if the visit date occurs on or after the reference date or Visit date minus Reference date if the visit date occurs before the Reference date, where the Reference date is defined as the first dose date (DY=1)
3. The change from baseline at a given Visit = observed value at that Visit minus observed value at baseline
4. ADHD-RS-5 total score =sum of scores for the 18 behaviors
5. ADHD-RS-5 Inattention subscale score = sum of scores for the first 9 behaviors
6. ADHD-RS-5 Hyperactivity/Impulsivity Subscale score = sum of scores for the last 9 behaviors
7. Conners 3-Parent Reported score: Composite T-score calculated by averaging over the 6 domains
8. Conners 3-Parent Reported score: T-score for individual domain: inattention, hyperactivity/impulsivity, aggression, executive functioning, learning problems, and relationships
9. Conners 3-Self Reported score domains: Composite T-score over the 5 domains
10. Conners 3-Self Reported score domains: inattention, hyperactivity/impulsivity, aggression, learning problems, and relationships
11. WFIRS-P score=average of all 50 items
12. WFIRS-P subscale scores: average of items of following 6 subdomains: Family, School (learning and behavior), Life Skills, Child's Self-Concept, Social Activities, and Risky Activities
13. PSI-4-SF: score=sum of all 36 items
14. PSI-4-SF: subscale scores: sum of items of following 3 subdomains: parental distress (PD), parent-child dysfunctional interaction (P-CDI), and difficult child (DC)

5 Study Variables

5.1 Primary Efficacy Variable

The ADHD-RS-5 is an ADHD-specific rating scale designed and validated to assess current ADHD symptomatology as described in the fifth edition of the Diagnostic and Statistical Manual of Mental Disorders (DSM-V). The scale consists of 18 items that directly correspond to the 18 DSM-V symptoms and are further subdivided into two subscales: Hyperactivity/Impulsivity and Inattentiveness ([DuPaul, 2016](#)). The ADHD-RS-5 scale rates the frequency and severity of each symptom on a 4-point Likert-type scale from 0 (none) to 3 (severe) and allows assessment of functional impairments linked to each symptom dimension. The ADHD-RS-5 rating scale is one of the most commonly used measures of drug efficacy in the treatment of ADHD and is the primary outcome measure for this study. The ADHD-RS-5 Home Version: Child instrument will be administered and scored by Investigator at each weekly visit from Baseline through EOS.

5.2 Secondary Efficacy Variables

5.2.1 Clinical Global Impression-Improvement

The CGI scale was developed to provide a brief, stand-alone assessment of the clinician's view of a subject's global functioning prior to and after administration of a SM ([Guy 1976](#)). The Clinical Global Impression – Severity of Illness (CGI-S) is a single item clinician rating of clinician's assessment of the severity of the ADHD symptoms in relation to the clinician's total experience with patients with ADHD. The Clinical Global Impression – Improvement Scale (CGI-I) is an assessment of how much the patient's illness has improved or worsened relative to a baseline state at the beginning of treatment. Both CGI-S and CGI-I are rated on a 7-point scale of 1 to 7 with 7 being "extremely ill" or "very much worse", respectively. Successful therapy is indicated by a lower overall score in subsequent testing.

CGI-I, relative to the condition at baseline, will be evaluated by the Investigator at each post-baseline visit on a 7-point scale with 1=Very much improved, 2=Much improved, 3=Minimally improved, 4=No change, 5=Minimally worse, 6=Much worse, and 7=Very much worse.

5.2.2 Conners 3

The Conners 3rd Edition™ (Conners 3) is a focused diagnostic tool for assessment of ADHD and associated learning, behavior, and emotional problems in children ages 6 to 18 years ([Sparrow, 2010](#)). The scale is based on the solid findings and key elements of its predecessor, the Conners Rating Scales-Revised (CRS-R™), but offers a more refined assessment of ADHD and comorbid

disorders (e.g., oppositional defiant disorder and conduct disorder). The Conners 3 instrument includes items related to inattention, hyperactivity, and impulsivity, as well as assessments of executive functioning, learning problems, and relationships. Like previous versions, the Conners 3 combines teacher, parent, and student reports to provide a particularly detailed and comprehensive evaluation of student behavior as observed in different settings. Teacher, parent, and self-report (for 8-18y.o.) rating scales are all available in long and short versions. The short forms of Parent, Teacher, and Self Reports of Conners 3 are comprised (respectively) of 45, 41, and 41 items. All Conners 3 scale versions are scored on a 4-point scale (0-3), where a higher score indicates more severe symptom presentation.

The Conners 3 scales will be administered at Visit 2 (Baseline) and at Week 8 (EOS) according to subjects' age as follows:

- Age 6-11: Conners 3 – Parent: Short (Conners 3-PS)
- Age 8-11 only: Conners 3 – Self-Report; Short (Conners 3-SRS)

5.2.3 WFIRS-P

The WFIRS instrument evaluates ADHD-related functional impairment ([Gajria, 2015, Thompson, 2017](#)). This scale allows the clinician to assess to what degree a patient's behavior and emotional problems affect his/her ability to accomplish daily tasks and interactions and helps to identify specific areas of difficulty. The scale has been validated in the ADHD population; the parent-based version completed by the parent/guardian of a child is used in this study and comprises 50 items grouped into six domains: Family, School (learning and behavior), Life Skills, Child's Self-Concept, Social Activities, and Risky Activities. The items relate to the past month and are scored using a 4-point Likert scale. Higher WFIRS-P scores indicate more severe functional impairment. This instrument will be completed at Baseline and EOS by the parent/caregiver.

5.2.4 PSI-4-SF

The Parenting Stress Index, Fourth Edition (PSI-4) questionnaire evaluates the magnitude of stress in the parent-child relationship based on the parent's perception of the child's characteristics, the personal characteristics of the parent, and the interaction between the parent and the child ([Abidin, 1995](#)). The short form of the PSI-4 (PSI-4-SF) consists of 36 items divided into three domains: parental distress, parent-child dysfunctional interaction, and difficult child. The PSI-4-SF scale was developed for parents of children ages 1 month to 12 years. This scale will be completed at Baseline and EOS by the parent/caregiver.

5.3 Pharmacokinetic Variables

5.4 Safety Assessments

Safety assessments include adverse events (AEs), clinical laboratory tests, vital signs, physical examinations, ECGs, and the Columbia Suicide Severity Rating Scale (C-SSRS).

6 Statistical Methods

6.1 General Principles

All statistical analysis will be performed using SAS version 9.2 or higher by [REDACTED], which is the designated CRO. [REDACTED] will be responsible for creating TLF reports by SAS programming and delivering the reports as well as the programs to Supernus at the completion of the study.

All tabulations of analysis results will include summaries for the following three treatments: SPN-812 ER 400 mg, SPN-812 ER 200 mg, and placebo.

Where appropriate, variables will be summarized descriptively (frequency count and percent for categorical variables, and number of subjects (n), mean, standard deviation (SD), median, minimum, and maximum for continuous variables).

Means, least-squares (LS) means and medians will be presented to 1 more decimal place than the recorded data. Standard deviations and standard errors will be presented to two (2) more decimal places than the recorded data. Minimum and maximum values will be presented using the same number of decimal places as the recorded data. Confidence intervals will be presented using the same number of decimal places as the parameters (e.g., mean). Percentages will be presented to one (1) decimal place. P-values will use four decimal places.

Categorical variables will be analyzed using categorical response methods such as Pearson's Chi-square test. If expected frequencies are too small for asymptotic assumptions, exact testing techniques will be used.

The data summaries will be accompanied by individual subject data listings, as specified in Sections 16.2 and 16.4 of ICH Guidance E3, sorted by unique subject identifier. All data available from the electronic case report forms (eCRFs) will be listed. Unscheduled measurements will be excluded from the descriptive statistics and statistical analysis but will be included in listings. The

“EARLY_TERMINATION VISIT” for early discontinued subjects will be assumed to correspond to Visit 10 for statistical summaries but displayed as is in listings.

Derived analysis datasets will be produced from the SDTM data. Specifications for derived datasets will be developed. Analysis datasets to be created will include ADQS (Questionnaire analysis dataset), ADEFF1 and ADEFF2 (efficacy analysis dataset2), ADSL (subject-level analysis dataset), ADAE (Adverse event analysis dataset) and other as appropriate.

The ADEFF1 analysis dataset will be used for programming the primary analysis table and will contain variables for Subject ID, BASE (Baseline (Visit 2)), AVAL (values at Visit 3 –Visit 10), CHG (for CFB), ITT Flag variable, Treatment, and other necessary variables to be created. For each subject there will be nine records associated with nine visits: Baseline and Visit 3 - Visit 10. The ADEFF2 analysis dataset will be created based on MI assuming MNAR for sensitivity analysis and MI assuming MAR for secondary analyses. The ADEFF2 will contain 100 imputations of each record of each visit for the variables in ADEF1 with IMPUTNR variable.

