6.2 Visit Windows

The Visit windows depicted in the table below will be used to evaluate subject compliance with scheduled visits with respect to protocol deviation. However, no visit windows will be used for statistical analysis; data will be analyzed according to the scheduled visit they are associated with in the CRF.

Table 2: Visit Windows and Study Day Ranges

Week	Day	Visit Window
0 (Visit 1-2)	1	<= Day 1
1 (Visit 2-3)	7	Day 2 - Day 9
2 (Visit 3-4)	14	Day 10 - Day 16
3 (Visit 4-5)	21	Day 17 - Day 23
4 (Visit 5-6)	28	Day 24 - Day 30
5 (Visit 6-7)	35	Day 31 - Day 37
6 (Visit 7-8)	42	Day 38 - Day 44
7 (Visit 8-9)	49	Day 45 - Day 51

8 (Visit 9-10)	56	Day 52 - Day 58
----------------	----	-----------------

For analysis by titration and maintenance period, the periods will be defined as follows: Titration period: First dose date \leq to \leq v5 date; Maintenance period: V5 date $<$ to \leq V10 date.

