6.17.2 Laboratory Data

The change from baseline will be calculated as post-baseline value minus baseline value.

For each laboratory parameter, the following will be displayed for baseline and Week 8 (EOS).

- Summary statistics (n, mean, SD, median, minimum, and maximum) by treatment group for the actual and change from baseline values will be presented in Tables 14.3.2.1.1 and 14.3.2.2.1.
- Laboratory values will be flagged as abnormally low (L) if the value $<$ lower limit of the normal range, normal (N) if the value is within normal range or abnormally high (H) if the value $>$ upper limit of the normal range. Shift tables for the change from baseline to endpoint Week 8 (EOS) will be presented in Tables 14.3.2.1.2 and 14.3.2.2.2. Laboratory data will be presented in Listings 16.2.8.1 and 16.2.8.2.

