16.17.4 Twelve (12)-Lead ECG

ECG parameters include HR, QRS, PR, and QTc.

If there is no original QTc in the database, then the QTc will be calculated using the following formulae:

$$\text{Fridericia's cube-root corrected QT : QTcF (ms)} = \text{QT (ms)} \times \sqrt[3]{\frac{\text{HR(bpm)}}{60}}$$

Table 4: Normal ECG ranges

Parameter, unit	Normal range	
	Lower limit	Upper limit
HR, bpm	60	140

PR, ms	90	170
QRS, ms	40	90

Source: <http://learn.pediatrics.ubc.ca/body-systems/cardiology/approach-to-pediatric-ecg/>

Values within boundaries and equal to the boundaries are still considered normal (N).

A value is classified as abnormally low (L) when the value < lower limit of the normal range.

A value is classified as abnormally high (H) when the value > upper limit of the normal range.

For the QT and QTc parameters, the following categorizations will be done:

- of the actual values: ≤ 450 ms, 450 ms < to ≤ 480 ms, 480 < to ≤ 500 ms, >500 ms
- of the changes from baseline: ≤ 30 ms (including all decreases in QT), $30 < to \leq 60$ ms, >60 ms.

ECG parameters will be summarized by treatment group using descriptive statistics (for quantitative ECG parameters) in Table 14.3.4.1 and frequency tables (for categorical parameters) in Table 14.3.4.2, Table 14.3.4.3, and Table 14.3.4.4.

Subject Listing of ECG: Parameters for actual and derived variables will be presented Listings 16.2.10.1 and 16.2.10.2.

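### The blanket exclusion of unscheduled measurements keeps any ECG taken between first dose and end of study out of the QT/QTc category tables

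*SAP*

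**What the plan says.** - **Unscheduled values.** SAP Section 6.1: "Unscheduled measurements will be excluded from the descriptive statistics and statistical analysis but will be included in listings". No exception is made for safety data or for baseline. The same section counts frequencies and percentages for categorical variables among its descriptive summaries, so the rule reaches frequency tables.
- **Assigning data to visits.** SAP Section 6.2: "no visit windows will be used for statistical analysis; data will be analyzed according to the scheduled visit they are associated with in the CRF". An unscheduled value therefore cannot be moved to a scheduled visit by its date.
- **ECG schedule.** Table 1 (Section 3.2) marks the 12-lead ECG at Visit 1 and Visit 10 only.
- **ECG outlier tables.** The ECG section (numbered 16.17.4 in the body) says: "For the QT and QTc parameters, the following categorizations will be done". Actual values are cut at 450, 480 and 500 ms, and changes from baseline at 30 and 60 ms. No visit is named.
- **Early discontinuation.** Section 3.3 has early discontinuers undergo the EOS procedures. Section 6.1 says the early termination visit "for early discontinued subjects will be assumed to correspond to Visit 10 for statistical summaries".
- **Baseline.** Section 4, item 1: "baseline is defined as the non-missing value collected most recent to and before the time of the very first dose of the SM". The item opens with a qualifier that lets other specifications override it. Section 6.17 applies this baseline to safety, with a similar qualifier.

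**The concern.** Leaving unscheduled values out of by-visit means is ordinary practice, because they have no visit to belong to. An outlier table has a different purpose: it counts how many subjects in each arm ever crossed a threshold. With no scheduled ECG between screening and EOS, the exclusion does not trim surplus repeats. It removes the only interim on-treatment ECGs that could exist.

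At stake is the between-arm count of marked QT/QTc values. Listings keep each value but give no counts by arm.

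A second, smaller issue is baseline. If a screening ECG is repeated at an unscheduled visit before the first dose, Section 4 points to the repeat, while Section 6.1 can be read as barring it. The change categories depend on which value is used.

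**Working it through.** The plan gives no figure to reproduce, so the check is a count of scheduled assessments in Table 1 and a comparison of sections.

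**1. Scheduled assessments after first dose and before EOS.** These are Visits 3 to 9, that is 9 − 3 + 1 = 7 visits (Days 7 to 49).

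| Assessment | Scheduled at Visits 3–9 | Scheduled elsewhere |
|---|---|---|
| ECG | 0 of 7 | Visits 1 and 10 |
| Hematology | 0 of 7 | Visits 1 and 10 |
| Serum chemistry | 0 of 7 | Visits 1 and 10 |
| Vital signs | 7 of 7 | Visits 1, 2 and 10 |

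In a subject who completes, any ECG between first dose and EOS is outside the schedule.

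**2. Which sentence removes an interim value from the tables?**

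- *ECG.* The QT/QTc categories name no visit, so nothing in the ECG section confines them to EOS. Section 6.1 does the excluding, and Section 6.2 offers no way back in by date.
- *Laboratory.* Section 6.17.2 limits its summaries to baseline and Week 8 (EOS), and its shift tables to the change between those two points. Interim values are out whatever Section 6.1 says.
- *Vital signs.* They are scheduled at every visit, so the argument does not apply.

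**3. A subject followed through the rules.** Suppose an unscheduled ECG shows QTc above 500 ms and a change above 60 ms, and the EOS ECG shows QTc at or below 450 ms and a change at or below 30 ms. The subject is counted in the lowest category of both tables. The interim ECG appears in the ECG listings (16.2.10.1 and 16.2.10.2) only. If the subject had stopped early, the early termination ECG would be counted as Visit 10, but the earlier unscheduled ECG would still be left out.

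**4. Baseline.** No ECG is scheduled at Visit 2, and screening may fall up to 28 days before it, so the only scheduled pre-dose ECG can be up to 28 days older than that visit. Section 4 is not restricted to scheduled values. Section 6.1 does not mention baseline. The SAP does not say which prevails if a repeat is recorded as unscheduled.

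**5. Size.** The SAP gives no number of unscheduled ECGs, so the effect on the counts cannot be calculated.

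**The case against.** The strongest reply is that the exclusion is prespecified and every excluded value is still listed. Selectively collected ECGs also bring a problem of their own: subjects examined more often have more chances to cross a threshold, so a worst-value table may reflect unequal ascertainment between arms. That stands as a reason for a footnote. It does not justify leaving the values uncounted, because listings cannot provide a comparison by arm.

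Several stronger readings may occur to a reader, and the SAP does not support them:

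- *That Section 6.1 also strips interim laboratory values from the shift tables.* Section 6.17.2 does that on its own. Deleting the sentence in 6.1 would add no laboratory value, and the SAP describes no separate laboratory outlier table.
- *That a mid-treatment QTc prolongation would appear in no table at all.* If reported as an adverse event, it could enter the tables in Sections 6.17.1.1 to 6.17.1.3, including the one for events leading to discontinuation. The event definition is in the protocol, which is not at hand.
- *That Sections 6.1 and 4 flatly contradict each other on baseline.* Section 4 yields to other specifications, so 6.1 could be taken as the override. Alternatively, Section 4 may govern derivation and 6.1 only what is summarized. Under Section 6.2, a repeat entered under Visit 1 in the CRF need not be unscheduled at all.
- *That abnormal values are undercounted precisely in the subjects in whom a problem was suspected.* This is plausible, but the SAP does not say why unscheduled ECGs would be taken.

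**Conclusion.** The point holds for ECG. Followed as written, the SAP keeps any unscheduled on-treatment ECG out of the QT/QTc frequency tables, and no ECG is scheduled between first dose and EOS. A value above 500 ms or a change above 60 ms that resolved by EOS would be uncounted in every ECG table. EOS and early termination ECGs are retained.

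The baseline question is an ambiguity to settle, not an error. The laboratory tables are limited by their own section, and vital signs are not affected in this way.

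The conclusion assumes that an interim ECG is recorded in the CRF as unscheduled. The number of subjects affected is unknown and may be zero. The efficacy analyses are not involved. This is a worthwhile and cheap improvement to the safety tables.

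**What to change.** 1. In Section 6.1, keep the exclusion for by-visit descriptive statistics and add an exception for the QT/QTc categories.
2. In the ECG section, state that these categories use each subject's worst value after first dose from scheduled and unscheduled ECGs: the highest actual value and the largest increase. With one baseline per subject and parameter, both come from the same ECG.
3. Footnote the tables to say that unscheduled ECGs may be unequally ascertained between arms.
4. In Section 4, state that an unscheduled pre-dose value may serve as baseline. This matters in practice because Section 7 has derived datasets programmed independently, and two programmers could now choose different baselines.
5. Optionally, add a laboratory shift from baseline to worst post-baseline value. This would be a new display alongside the one in Section 6.17.2, not a repair of Section 6.1.

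The cost is a few sentences of SAP text and minor programming on data already collected. The by-visit summaries and the efficacy analyses do not change. The downside is the possible ascertainment imbalance, which the footnote discloses but does not remove.
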